#### **Research Design and Methods Overview (Aims # 4)**

**Aim #4: to determine the intervention's budgetary impact.** Research Question: **What are the budgetary impact costs associated with the intervention and how do these costs compare to the costs of standard care?** Data collection & measures: We will obtain cost data in the VA Managerial Cost Accounting System (MCAS) (formerly DSS) National Data Extracts (NDE) (total, nursing, pharmacy, laboratory, etc.) by fixed and variable categories and the Non-VA Medical Care (formerly fee-basis) files, supplemented by the direct measures (i.e., microcosting) of the intervention as necessary. The budgetary impact of this intervention will consist of two parts: (1) the incremental cost of the intervention itself over and above usual care, and (2) the impact of the intervention on healthcare utilization. To determine the incremental costs of the intervention, we will use micro-costing techniques (viz., direct measurement and pseudo-billing)[82] combined with average costing [83] to determine the average staff time, wage, space, and equipment costs associated with the intervention. We will pay particular attention to capturing the full operational costs of the intervention to include items such as the costs and amortization of equipment, network devices, all associated maintenance costs. Simultaneously, we will take care to exclude any costs associated exclusively with our research (e.g., resources expended solely for purposes of research data collection) so that our results will reflect accurately those costs likely to be incurred in a purely clinical, non-research setting. The micro-cost estimate for the intervention will use the average elapsed time of the sessions along with an estimate of the average national wage [84] of the type of clinician most likely to deliver the intervention in the field.

To determine the intervention's impact on the costs of healthcare utilization, we will rely on ISPOR's 2014 budgetary impact analysis guidelines.[85] Data on VA utilization costs will be obtained from MCAS the Decision Support System National Data Extracts (DSS NDE) [86] and the Non-VA Medical Carefee-basis files.[87] We will tabulate all costs from these sources for study enrollees over the period of the study, calculate the difference between intervention and standard care average costs and test for the statistical significance of this difference using the Z-score method proposed by Zhou.[88] The final step in determining the budgetary

impact of the intervention will combine parts 1 and 2 to determine the complete impact of the intervention on the VA budget. While the incremental cost of the intervention (part 1) will be positive, the impact of the intervention on the costs of VA utilization will likely vary directly with the impact of the intervention on VA utilization.

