### Intervention

Participants in the intervention group will participate in 8 weekly telephone sessions with an interventionist. The telephone-based intervention consists of a problem-solving telephone support educational intervention led by a trained interventionist. The intervention’s main objective is to reduce caregiver burden and depressive symptoms by teaching caregivers a creative and optimistic approach to solving caregiving related problems. The intervention will utilize the problem solving module and refer to additional information/tools on the Spanish RESCUE website (<http://www.cidrr8.research.va.gov/rescue-espanol/>). The information included in the intervention consists of: 1. Introduction, 2. Illustrative Example, 3. Individualized Practice Exercise, and 4. Summary.

The intervention is adapted from the intervention used in our previous pilot project and based on the work of Bakas et al.,[23] who conducted a successful 8-week telephone intervention which used support approach and a task skill-building kit (TASK). In this proposed project we will tailor our pilot intervention to be culturally relevant for a Puerto Rican population. The intervention was developed to reflect specific characteristics of the target population such as language, cultural values and norms, and degree of acculturation. To enhance the cultural relevance of the intervention, we will use findings from our previous projects and guidelines from authoritative sources [55] that recommend: 1) involving persons from the target population in all phases of the project (e.g., Advisory Consortium), 2) emphasizing themes that are valued by the PR culture (e.g., family, religion, self-reliance), 3) assuring that the language and wording of on-line information is low-literate and appropriate by enlisting services of certified translators and Spanish-speaking experts, and 4) conducting the intervention and assessments by hiring research staff members (i.e., interventionist, data collector) who are Hispanic, fluent in Spanish, and knowledgeable about the PR culture. Research consistently shows that matching interventions to the individual needs of participants is more effective in engaging adults and modifying behaviors than prescriptive approaches.,[16] Other studies underscore the benefits of interventions and programs that are tailored to a specific race/ethnic populations.[55]

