| 
Topic 3: Individualized Practice Exercise Session
 
Developing a Personalized Problem-Solving Plan
   | 
The interventionists will assist the caregivers in developing their own personalized plans.
 
Step one: The interventionists and the caregivers together will identify all potential problems. To accomplish this step, the interventionists will use motivational interviewing[56] and encourage the caregivers to talk about their uncertainties and what problems they expect to face when their survivors go home. The interventionists will use information learned from the Veterans' health record to help caregivers identify problems. As needed, the interventionists will review the list of 45 topics/factsheets that are on the RESCUE website to trigger identification of problems.
 
Step two: Caregivers will use the "RESCUE workbook" that includes a "problem-solving diary." The caregivers with guidance from the interventionists will use the diary to write down all their problems, prioritize problems, and identify the most troublesome problem. This problem-solving diary can be accessed and printed from the RESCUE website.
   |

|  |   |
|--|---|
| (Sessions 3 - 7)  | Step three: The caregivers will read and discuss the factsheet (s) on the RESCUE caregiver website related to their most troublesome problem. With guidance from the interventionists, the caregiver will use the problem-solving diary to list realistic goal(s), possible solutions, best solution, and evaluation plans.  |
| Topic 4: Summary of the Problem-Solving Method (Session 8) | The interventionists will summarize the content from the previous sessions and answer questions for clarification. The interventionists will encourage the caregivers to use the problem-solving approach and diary to address future problems. The interventionists will review log-on procedures (see details under "workbook" section) and how to navigate and find information and tools on the RESCUE website. |

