**RESCUE Problem-Solving Diary Form:** As noted in the table, the interventionists will collaborate with the caregivers in writing their personalized plans on a problem-solving diary. The form provides spaces for the caregivers to list and prioritize their problems and spaces for their goals, solutions, and evaluations. Caregivers will be instructed to go to the RESCUE website and print the blank diary forms as needed. We will mail workbooks to caregivers in the intervention group.

**Standard Care Group:** Will consist of caregivers who receive the care that is normally provided to stroke caregivers of Veterans. No changes will be made in the care that these caregivers normally receive. We will carefully document all follow up care (after Veterans' discharge) by reviewing the Veterans' record and asking caregivers to discuss any care they or their Veteran received. According to clinicians who provide services in the VACHS to Veterans with stroke and their caregivers, once the Veteran is discharged to the home, caregivers do not normally receive any follow-up telephone or transitional care unless they are enrolled in the Telehealth or home-based primary care programs (study exclusionary criteria). Stroke caregivers may only receive contact information for stroke clinicians and some may receive informational brochures or an invitation to participate in an open support group led by the psychologist in the rehabilitation clinic. At the end of the study, we will ask caregivers in the standard care group about resources used throughout the study.

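### Aim 4 sets out to capture full delivery cost, but names session time as its only labour quantity and plans no record of delivery work outside the call

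*Combined protocol and SAP*

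**What the plan says.** The section Research Design and Methods Overview (Aims # 4) divides the budget impact into two parts, later combined: the incremental cost of the intervention over usual care, and its effect on the cost of healthcare use.

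For the first part the stated scope is broad. Micro-costing and average costing are to be used "to determine the average staff time, wage, space, and equipment costs associated with the intervention". The plan adds: "We will pay particular attention to capturing the full operational costs of the intervention". The examples that follow are equipment, network devices and maintenance. Costs incurred only for research are to be left out: the team will "exclude any costs associated exclusively with our research".

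The paragraph then ends with the one working rule for labour: "The micro-cost estimate for the intervention will use the average elapsed time of the sessions", together with an estimated national average wage for the clinician type most likely to deliver the programme in the field.

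On time data, the Intervention section says call length will be documented, and Fidelity Considerations says contact minutes will be recorded for each participant. No section describes a record of staff time outside the call.

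**The concern.** The scope and the working rule do not match. A programme of this kind uses staff time that is neither call time nor research, and the protocol describes several examples. If labour is costed from session time alone, that work drops out of the first part of the budget impact and so out of the combined figure.

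Staff time is central to this aim. The Abstract says that earlier problem-solving interventions were little used in practice partly because of the staff time they demand, and the long-term goal is use throughout the VHA. A cost figure that leaves out recurring delivery labour would understate what a site has to provide. Time that nobody logs during delivery is also harder to measure well afterwards.

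**Working it through.** The documents give no cost, wage or staff-hour total for Aim 4, so there is no figure to reproduce. The check sets the described work against the planned data, then illustrates the size.

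**Delivery work outside the call, and whether its time is captured**

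- Veteran's record. Topical Content, Topic 3: "The interventionists will use information learned from the Veterans' health record to help caregivers identify problems". Someone must read the record; the role is not named. No time record is planned.
- Workbooks. The paragraph on the diary form says: "We will mail workbooks to caregivers in the intervention group". Topic 1 says each holds directions for a unique web address and a calendar of agreed session dates, so preparation and scheduling are implied. The role is not named. No time record is planned.
- Scheduling. Data collection procedures says sessions are held at times that suit the caregiver. No time record is planned.
- Training and escalation calls. Section 7 describes both for the interventionist. No time record is planned.

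**Illustrative size**

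Inputs from the documents:

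- Number of sessions: "Participants in the intervention group will participate in 8 weekly telephone sessions with an interventionist".
- Expected call length: 45 to 60 minutes (Intervention section).

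Assumed input: off-call delivery minutes per session, p = 5, 10 or 20. The documents give no value.

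Contact minutes for a caregiver who completes all sessions: 8 × 45 = 360 to 8 × 60 = 480, or 6 to 8 hours.

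Off-call minutes, 8 × p: 40, 80 or 160.

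Addition to staff time, (8 × p) / contact minutes:

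| p (assumed) | 60-minute calls | 45-minute calls |
|---|---|---|
| 5 | 40/480 = 8% | 40/360 = 11% |
| 10 | 80/480 = 17% | 80/360 = 22% |
| 20 | 160/480 = 33% | 160/360 = 44% |

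As a share of full staff time, the omission runs from 40/(480 + 40) = 7.7% to 160/(360 + 160) = 31%.

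Spreading p over all eight sessions is itself an assumption. Topic 3, where use of the record is described, covers sessions 3 to 7. If p applied to those five sessions only, the addition would run from 25/480 = 5% to 100/360 = 28%, before any one-off workbook time.

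**Direction**

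Leaving out off-call time can only lower the staff cost. The number of sessions charged is a separate matter. If average call length were multiplied by eight for everyone, a caregiver who completed six 45-minute calls (an assumed case) would be charged 360 minutes for 6 × 45 = 270, which is 90 too many. That error runs upward. The plan does not say that it will multiply by eight.

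**The case against.** The strongest reply is that the labour sentence says what the estimate will use, not that it will use nothing else. The same paragraph commits to direct measurement of staff time and to completeness, with an open list of examples. A reader might infer that the plan excludes off-call labour and that the cost figure is therefore certain to be too low. The text does not support that: there is no express exclusion, and the general wording leaves room for such time.

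Other parts of the reply also stand:

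- Record review and mailing are not assigned to the interventionist.
- Some of the work may be research-only and rightly left out. Data collection procedures has the team reviewing Veterans' records for the study, and the workbook carries study details, the consent statement and the post-test date.
- Total contact minutes per caregiver are already to be recorded, so that part of a better unit is in hand.
- A continuous log is not the only remedy. The plan allows direct measures where needed, so a timed sample could serve.
- Further detail may lie in the cited costing methods, which cannot be checked from these documents.

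What does not stand is the suggestion that the general promise closes the gap. Session time is the only labour quantity named, the examples of full cost include no labour, and nothing says how off-call delivery time would be obtained.

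**Conclusion.** The concern holds as a mismatch within Aim 4 that carries a conditional bias. Applied as written, the labour rule leaves recurring delivery work out of the staff-time component of the incremental cost, and that component is then too low.

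The size is unknown. The 8% to 44% range rests wholly on the assumed 5 to 20 off-call minutes in each of eight completed sessions. It concerns staff time; the percentage effect on the whole first part, which also includes space, equipment and maintenance, cannot be derived from the documents. It should not be read as an estimate for this trial.

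A reader might also infer that every error in the labour costing favours the intervention. That is true only of the off-call omission, since charging eight sessions to all caregivers would err the other way.

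The point does not touch the primary endpoint or any effectiveness analysis. It is still worth correcting, because the cost figure is meant to inform wider use and the remedy is small.

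**What to change.** In the Aim 4 section, replace the rule based on average session time with total delivery-staff minutes per caregiver, averaged over all caregivers randomised to the intervention. The total should comprise:

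- contact minutes, already to be recorded under Fidelity Considerations, which also settles the session-count question;
- off-call delivery minutes for record use, workbook preparation and mailing, scheduling and escalation calls;
- interventionist training, amortised per caregiver.

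Add an off-call minutes field to the existing record of contact minutes, or time a sample of caregivers. For each entry, note the activity, the staff role and whether the work is delivery or research-only. Value the minutes at the wage for that role, and exclude the research-only minutes as the plan already intends.

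The cost is one field on an existing record, or a short timing exercise, and a rewritten sentence in Aim 4. The drawbacks are slightly more logging and a somewhat less favourable cost figure.

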**Fidelity Considerations:** We will make special effort to enhance, maintain and track treatment fidelity. We will use recommendations of Borelli, et al.,[63] and Burgio et al.[64] as our guide. We will adapt the standardized manuals and protocols that were used in our pilot project. This manual will provide step-by-step guidelines on recruiting/enrolling participants, implementing the informed consent process, in conducting the intervention and implementing the data collection procedures. We will provide extensive training to all of our team members. [name] will periodically observe the interventionists conducting the telephone intervention. We will have monthly meetings with the interventionists to discuss implementation of the intervention and discuss protocol issues. To monitor the delivery of the intervention we will audio-tape (digitally record) 10% of the telephone sessions throughout the duration of the project with oral consent from the study participants (Consent will be obtained orally because we are requesting a HIPAA Waiver and Waiver of Documentation for Informed Consent). We will also record the number of minutes spent with each participant and to keep detailed notes of any deviations from our study protocol. The PI and data collector will review these audiotapes and evaluate adherence to study protocols, noting all deviations on a form. Feedback will be provided as needed.

Similar to Bakas, et al.,[23] we will evaluate "enactment" by asking caregivers (in intervention group) after completion of the study (at 12 week post-intervention time-point) to rate the amount of information and contact they received during the 8-session intervention, how much they used the skill-building strategies and the RESCUE website, how helpful the intervention was and whether their problems were resolved.

**Measures:** We carefully chose measures that had been translated into Spanish, used in previous research studies, had good psychometric properties, were easy to administer, and were relatively short in length to reduce participant burden. Most of the measures selected were tools that our team members had used previously in other studies. In the table below, we describe the measures we will use for screening caregivers to determine their study eligibility as well as the measures related to testing hypotheses 1-3. Our other measures are described in later sections. See proposed instruments below.

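### Aim 4 tests only the care-cost difference; the combined budget figure has no planned interval, and a test of care cost against zero does not test the net cost

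*Combined protocol and SAP*

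**What the plan says.** The Aim 4 overview in section 6 defines the budget impact as "1) the incremental cost of the intervention itself over and above usual care, and (2) the impact of the intervention on healthcare utilization".

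Part 1 is built from averages. The micro-cost estimate "will use the average elapsed time of the sessions along with an estimate of the average national wage", and the text adds space, equipment, amortisation, network devices and maintenance. No variance or range is given for any of these inputs.

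For part 2 the team states that "we will rely on ISPOR's 2014 budgetary impact analysis guidelines". It will tabulate each enrollee's VA and non-VA care costs, "calculate the difference between intervention and standard care average costs and test for the statistical significance of this difference using the Z-score method". This is the only statistical inference described under Aim 4.

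The final step "will combine parts 1 and 2 to determine the complete impact of the intervention on the VA budget". The plan adds: "While the incremental cost of the intervention (part 1) will be positive". It does not say how the parts are combined. It states no standard error, confidence interval, bootstrap or sensitivity analysis for part 1, part 2 or the total.

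Under Fidelity Considerations the plan also says: "We will also record the number of minutes spent with each participant".

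**The concern.** The quantity reported to the VA is the net of the two parts, but the planned test looks at one part only. Its null hypothesis is that care costs do not differ between arms. The budget question is whether any care-cost saving is larger than the cost of delivering the intervention. As part 1 is expected to be positive, these are different hypotheses, and a p-value for the first does not carry over to the second.

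Without an interval, a reader of the net figure cannot tell a well-determined saving or cost from one that the trial could not resolve. Budget impact is a named study objective, and the stated long-term goal is use of the intervention throughout the VHA. A bare figure could mislead that decision in either direction.

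**Working it through.** **The plan's own figure.** Aim 4 states no precision, cost SD or expected saving. The only sizing figure is for the CES-D (Sample Size and Power Analysis): difference 3.1, SD 8.9, 5% level (two-sided under Hypothesis 1), 80% power.

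- n per group = 2 × (1.96 + 0.84)² × 8.9² / 3.1² ≈ 2 × 7.85 × 79.21 / 9.61 ≈ 129.4, rounded up to 130.
- With 10% dropout: 130 / 0.90 = 144.4, rounded up to 145 per group.

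This matches the plan, but it says nothing about cost.

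**Inputs for Aim 4.**
- Total sample 227 (Sample section). Blocked randomisation to balanced groups is read as 1:1, so 113.5 per arm.
- Loss of 10% leaves about 204, or 102 per arm.
- SD is the between-Veteran standard deviation of care cost. It is not given in the documents, so results are in SD units.

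**Notation.** Let c be the part 1 cost per caregiver (c > 0) and D the difference in mean care cost, intervention minus standard care. Then net = c + D. The planned test is of D = 0. A net of zero corresponds to D = −c.

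**Precision of the net.** Treating c as fixed, SE(net) = SD × √(2/n per arm).

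| Analysed | SE | 95% half-width (1.96 × SE) |
|---|---|---|
| 227 | 0.133 SD | 0.26 SD |
| 204 | 0.140 SD | 0.27 SD |
| 290 (145 per group, as in the power paragraph) | 0.117 SD | 0.23 SD |

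The result therefore hardly depends on which of the plan's sample sizes is used.

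**What each analysis can show.** Take the Z test to behave like an ordinary comparison of two means; its formula is not in the documents. With 227 Veterans:

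- The Z test declares a care-cost saving when the saving exceeds 0.26 SD.
- The net estimate is a saving when the care-cost saving exceeds c.
- The 95% interval for the net lies wholly on the saving side only when the care-cost saving exceeds c + 0.26 SD.

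A care-cost saving between 0.26 SD and c + 0.26 SD is thus significant on the planned test, yet a net saving is not established. If c is above 0.26 SD, a saving between 0.26 SD and c is significant while the net estimate is a cost. The mismatch also runs the other way: if D is estimated as zero and c exceeds 0.26 SD, the Z test is non-significant although the net is clearly a cost.

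**Chance of the wrong sign.** P(wrong sign) = Φ(−|true net| / SE), with SE = 0.133 SD:

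| True net (SD) | 0.05 | 0.10 | 0.20 | 0.26 |
|---|---|---|---|---|
| P(wrong sign) | 35% | 23% | 7% | 2.5% |

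**In dollars, by assumption only.** Assume no true care-cost effect, so the true net is c and an estimated saving has the wrong sign. Neither the SDs nor the values of c come from the documents.

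| Assumed SD | 95% half-width | P(estimated saving), c = $500 | P(estimated saving), c = $2,000 |
|---|---|---|---|
| $1,000 | $260 | <0.1% | <0.1% |
| $5,000 | $1,301 | 23% | 0.1% |
| $10,000 | $2,602 | 35% | 7% |
| $20,000 | $5,204 | 43% | 23% |

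**The case against.** The best defence is the cited budget impact guideline, which may itself cover uncertainty and the step from enrollees to a budget. Its content is not in the documents, so this cannot be checked. The plan cites it for the care-cost part only, and a citation does not fix how the net is to be estimated or its uncertainty reported. The guideline deserves acknowledgement, but it does not close the gap.

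Second, the plan says only that the parts are combined. That bare averages will be added is an inference, and what can be said is that no measure of uncertainty is stated. The plan also gives no decision rule, and nothing in it says that a non-significant Z would be read as no budget effect.

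Third, pricing the sessions from average time and a national wage is a deliberate choice, meant to reflect delivery outside research. It can stand. If delivery cost varies little beside care cost, each caregiver's own minutes will barely change the interval, and an interval for part 2 shifted by c would be nearly the same.

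Fourth, a reader might infer that the sign of the net figure will probably be settled by chance. The documents do not support that. They give no cost SD, delivery cost or expected saving. Over the assumed range above, the chance of a wrong sign runs from under 0.1% to 43%, and it stays below 50% whenever the true net is not zero. Comparing care-cost noise with call labour alone would also understate part 1, which includes non-labour items.

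**Conclusion.** The concern holds as a mismatch between the test and the quantity reported, together with a missing interval. The planned test addresses part 2 against zero; the reported figure is part 1 plus part 2, with part 1 expected to be positive.

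With 227 Veterans the trial can place the net only to within about ±0.26 SD of care cost (±0.27 SD after 10% loss). This assumes 1:1 allocation, delivery cost treated as fixed, a normal approximation and, for the first figure, complete cost data. If the estimated net is smaller than that, its sign is unresolved; if it is larger, the sign is fairly secure. Which case applies cannot be known from the documents, and no dollar size should be quoted as a result of this review.

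The change should be made, but its weight is modest: Aim 4 is not the primary aim, and the depression analysis is unaffected.

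**What to change.** Make the main Aim 4 result the between-arm difference in mean net cost per randomised caregiver. Net cost is the Veteran's care cost plus, in the intervention arm, the full delivery cost as the plan defines it, including space, equipment and maintenance as well as staff time. Report it with a 95% confidence interval, for example from a bootstrap that resamples participants within arm. Recorded minutes can supply the time component, valued at the national wage already planned.

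Add sensitivity ranges for the wage and equipment inputs, because resampling participants does not capture their uncertainty. The Z test on care cost can remain as a supporting analysis.

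If the result is scaled to a VA budget figure, show it over a range of assumptions for the eligible population and uptake. The documents give neither, so these would have to be sourced.

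The cost is a paragraph of SAP text and a short program. The per-caregiver analysis needs no new data collection, since minutes and costs are already to be obtained. The downside is an interval that may be wide and a result that looks less definite.
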